### Sensitivity analysis

A sensitivity analysis will be performed by repeating the primary analysis by imputing any missing values of weight/height/BMI at visit LT 18 by LOCF method from visit LT 17. Other missing values in the data will not be imputed.

### Secondary analysis

The analysis of secondary endpoints will be similar to the primary analysis. The secondary endpoints, changes in weight, height, BMI from baseline to end of study, will be analysed by hypertension group.

The estimated change from baseline and the 95% confidence interval for the difference between treatment groups at end of study will be presented for each hypertension group.

### **1.2.6.2 Neurocognitive assessments**

Neurocognitive assessments were performed only for patients with secondary hypertension at visit LT 18 (week 104) and visit LT 19 (week 156) in this study and therefore, the corresponding tables will include the secondary hypertension patients only.

Descriptive statistics for visit LT 17 (week 52), visit LT 18 (week 104), visit LT 19 (week 156) and change from baseline and visit LT 17 (week 52) of neurocognitive development evaluations collected will be presented. Visit LT 17(week 52) will be end of study visit from CSPP100A2365E1 study. In addition, number and percentage of patients with positive change, negative change and no change in percentages from baseline and visit LT 17 (week 52) to visit LT 18 (week 104), and visit LT 19 (week 156) for all neurocognitive tests will be presented.

### **1.2.7 Analysis of secondary variables**

#### **Adverse events**

The assessment of safety will be based primarily on the frequency of SAEs occurring within the first 30 days after the patient has completed study CSPP100A2365E1 (defined as time of last dose of study drug taken or last visit whichever is later). SAEs experienced after this 30 day period were reported to Novartis only if the investigator suspected a causal relationship to the study drug.

**Occurrence and frequency of SAEs collected will be summarized by treatment regimen in CSPP100A2365E1, primary organ class and preferred term**

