7.1 Adverse events

This trial will **only collect the occurrence of serious adverse events** as defined below and in [Section 7.2](#). An SAE is defined as an event which:

- is fatal or life-threatening
- results in persistent or significant disability/incapacity
- constitutes a congenital anomaly/birth defect
- requires inpatient hospitalization or prolongation of existing hospitalization, unless hospitalization is for:
 - routine treatment or monitoring of the studied indication, not associated with any deterioration in condition
 - elective or pre-planned treatment for a pre-existing condition that is unrelated to the indication under study and has not worsened since the start of study drug
 - treatment on an emergency outpatient basis for an event not fulfilling any of the definitions of a SAE given above and not resulting in hospital admission
 - social reasons and respite care in the absence of any deterioration in the patient's general condition
- is medically significant, i.e. defined as an event that jeopardizes the patient or may require medical or surgical intervention to prevent one of the outcomes listed above

Unlike routine safety assessments, SAEs are monitored continuously and have special reporting requirements; see [Section 7.2](#).

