7.2 Serious adverse event reporting

To ensure patient safety, every SAE, regardless of suspected causality, occurring until 30 days after the patient has completed study CSPP100A2365E1 (defined as time of last dose of study drug taken or last visit whichever is later) must be reported to Novartis within 24 hours of learning of its occurrence.

Any SAEs experienced after this 30 day period should only be reported to Novartis if the investigator suspects a causal relationship to the study drug.

Within this 30 day period, recurrent episodes, complications, or progression of the initial SAE must be reported as follow-up to the original episode, regardless of when the event occurred. This report must be submitted within 24 hours of the investigator receiving the follow-up information. An SAE that is considered completely unrelated to a previously reported one should be reported separately as a new event.

SAE information is collected and recorded on the Serious Adverse Event Report Form. The investigator must assess the relationship of any SAE to study drug, complete the SAE Report Form in English, and send the completed, signed form by fax within 24 hours to the local Novartis Drug Safety and Epidemiology Department. The telephone and telecopy number of the contact persons in the local department of Clinical Safety and Epidemiology, specific to the site, are listed in the investigator folder provided to each site. The original copy of the SAE Report Form and the fax confirmation sheet must be kept with the case report form documentation at the study site.

Follow-up information is sent to the same person to whom the original SAE Report Form was sent, using a new SAE Report Form stating that this is a follow-up to the previously reported SAE and giving the date of the original report. The follow-up information should describe whether the event has resolved or continues, if and how it was treated, whether the blind was broken or not, and whether the patient continued or withdrew from study participation.

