9.5.3 Safety variables

The assessment of safety will be based primarily on the frequency of SAEs occurring within the first 30 days after the patient has completed study CSPP100A2365E1 (defined as time of last dose of study drug taken or last visit whichever is later). SAEs experienced after this 30 day period are to be reported to Novartis if the investigator suspects a causal relationship to the study drug.

Occurrence and frequency of SAEs collected within this timeframe will be summarized by treatment regimen in CSPP100A2365E1, primary organ class and preferred term, and will be narrated if any.

Summary statistics by treatment regimen in CSPP100A2365E1 and visit for laboratory values (in patients with secondary hypertension only) will be provided. Occurrence of significant abnormalities in laboratory values from baseline will be summarized by treatment regimen in CSPP100A2365E1.

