**1.2.3 Medical history**

The number of patients with relevant medical history and/or continuing medical conditions collected at Week 2 (Visit 6) of the extension study (CSPP100A2365E1) and adverse events collected during the extension study (CSPP100A2365E1), regardless of whether they are resolved or on-going at the start of the CSPP100A2365E2, will be combined and summarized by primary system organ class, preferred term, and treatment regimen for the EFS. If there are

any on-going AEs in the CSPP100A2365E1 study which are on-going at the start of CSPP100A2365E2 and have changed in severity during CSPP100A2365E2, it is assumed that they will be reported as new AEs in CSPP100A2365E2.

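### The SAP drops the protocol's time limit on the SAE summary, so its only SAE table by regimen mixes two capture rules and none gives the 30-day frequency on which safety is mainly judged

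*SAP*

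**What the plan says.** E1 is study CSPP100A2365E1; E2 is the present off-therapy follow-up.

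**Collection.** Protocol 7.2 sets two rules. The first covers "every SAE, regardless of suspected causality, occurring until 30 days after the patient has completed study CSPP100A2365E1". The second applies from then on: "Any SAEs experienced after this 30 day period should only be reported to Novartis if the investigator suspects a causal relationship" to the study drug. The SAP restates the second rule under Adverse events: "SAEs experienced after this 30 day period were reported to Novartis only if the investigator suspected a causal relationship".

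**Basis of the assessment.** The SAP, like protocol 9.5.3, puts the weight on the early window: "The assessment of safety will be based primarily on the frequency of SAEs occurring within the first 30 days" after E1 completion. Completion is the last dose or the last visit, whichever is later.

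**Tabulation.** Protocol 9.5.3: "Occurrence and frequency of SAEs collected within this timeframe will be summarized by treatment regimen". SAP 1.2.7: "Occurrence and frequency of SAEs collected will be summarized by treatment regimen". Both then break the summary down by organ class and preferred term. The SAP sentence carries no time window and no split by period or causality, and it leaves out the protocol's provision for narratives.

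**A related passage.** Of ongoing E1 adverse events whose severity changes during E2, SAP 1.2.3 says "it is assumed that they will be reported as new AEs in CSPP100A2365E2". Protocol 7.1 says that the trial will "only collect the occurrence of serious adverse events".

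**The concern.** An SAE table has a clear meaning only if every event in it was captured under the same rule. Here the rule changes at day 30. Before it, the count includes every SAE; after it, the count includes only events that passed a causality judgement. Put over one denominator, the two give a percentage that answers neither obvious question: how often SAEs occurred shortly after E1, or how often they occurred during follow-up.

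The protocol's limit avoids this and the SAP's wording does not. A programmer working from SAP 1.2.7 would build one table of everything in the database and would not build the 30-day table. The stated main basis of the safety assessment would then have no output behind it. A reader could also take the combined percentage for the 30-day figure, which is too high a reading, or for the all-cause figure over one or two years, which is too low.

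**Working it through.** The documents give no SAE rate, no sample size and no share of SAEs expected to be judged drug-related, so there is no planned figure to reproduce. The check compares the texts and then does window arithmetic.

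**1. Texts side by side**

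| | To day 30 after E1 | After day 30 | Scope of the summary |
|---|---|---|---|
| Protocol 7.2 and 9.5.3 | all SAEs | suspected-related only | limited to a stated timeframe |
| SAP 1.2.7 | safety based mainly on these | suspected-related only | all SAEs collected |

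In protocol 9.5.3 the words about the timeframe follow a sentence on later SAEs, so they are slightly ambiguous. The 30-day window is still the natural reading: it is the only bounded period named there.

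**2. Length of the all-causality window**

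Inputs: protocol Table 3-1 puts the visits at LT days 365, 730 and 1095. Follow-up L is therefore 365 days in primary and 730 days in secondary hypertension. I take day 365 as the end of E1.

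- Primary: 30/365 = 8.2%
- Secondary: 30/730 = 4.1%

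**3. What the combined table would hold**

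Assumptions: a constant SAE hazard, and a share q of later SAEs that investigators suspect are drug-related. Neither comes from the documents.

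- Share of all SAEs captured = [30 + (L − 30)q] / L
- Share of the table arising after day 30 = (L − 30)q / [30 + (L − 30)q]

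| q | Captured, primary | Captured, secondary | Late events in table, primary | Late events in table, secondary |
|---|---|---|---|---|
| 0.05 | 12.8% | 8.9% | 35.8% | 53.8% |
| 0.10 | 17.4% | 13.7% | 52.8% | 70.0% |
| 0.20 | 26.6% | 23.3% | 69.1% | 82.4% |

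For q = 0.10 in primary hypertension: (30 + 33.5)/365 = 17.4%, and 33.5/63.5 = 52.8%. In secondary: (30 + 70)/730 = 13.7%, and 70/100 = 70.0%. The captured shares follow from the protocol's reporting rule. The mixing within one table follows from the SAP's wording.

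**4. Effect on the comparison of regimens**

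Let s be the share of a regimen's patients with secondary hypertension (assumed). With equal true SAE rates, expected captured events per patient are proportional to E(q, s) = 30 + [335(1 − s) + 700s]q, where 335 = 365 − 30 and 700 = 730 − 30.

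- Same q and same s in both regimens: ratio 1.00. A true rate ratio of 2 is shown as 2.00.
- q of 0.20 v 0.10, s = 0.30 in both: (30 + 444.5 × 0.20)/(30 + 444.5 × 0.10) = 118.9/74.45 = 1.60.
- q of 0.10 v 0.05, s = 0.30 in both: 74.45/52.225 = 1.43.
- q = 0.10 in both, s of 0.40 v 0.20: (30 + 48.1)/(30 + 40.8) = 78.1/70.8 = 1.10.
- q = 0.20 in both, s of 0.40 v 0.20: (30 + 96.2)/(30 + 81.6) = 126.2/111.6 = 1.13.

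Mixing alone does not distort the contrast. A difference between regimens in attribution or in etiology mix does.

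**The case against.** The strongest reply is that combining the two periods is inferred from an omission. The SAP never says that it will pool them. It keeps the sentence that makes the first 30 days the main basis and discloses the causality filter that follows. SAP section 1 says that data are analysed according to protocol section 9, and the document history claims consistency with the final protocol. On that view the protocol's limit still governs. This has some force: intent to pool is not shown. But a general cross-reference does not settle what goes into a table whose own sentence has been reworded without the limit, and no 30-day table is specified anywhere in the SAP.

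Three further points for the plan stand:

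- The SAE summary is descriptive, listed among the secondary variables and carries no hypothesis test.
- The same capture rule applies to both regimens. A reader might infer that the table is biased between aliskiren and enalapril. The documents do not support that: the ratio is 1.00 under equal attribution and equal etiology mix, and nothing shows that either differs. E1 was double-blind; protocol 5.4 calls blinding not applicable here, yet 7.2 still asks whether the blind was broken. Whether investigators know the regimen during follow-up is not stated.
- A reader might also blame the SAP for missing SAEs after day 30. That gap comes from protocol 7.2, and no tabulation can recover events that were never reported.

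The mismatch in SAP 1.2.3 concerns the medical history summary. It has no effect on the SAE table and adds no weight to the main point.

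**Conclusion.** The point holds as a discrepancy between the SAP and the protocol with a practical consequence. As worded, SAP 1.2.7 yields one SAE table by regimen that mixes all-causality events to day 30 with suspected-related events afterwards, and no table of the 30-day frequency.

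The all-causality window is 8.2% of planned follow-up in primary and 4.1% in secondary hypertension; these figures rest only on the visit days. If 5% to 20% of later SAEs were suspected, late events would make up about 36% to 69% of the table in primary and 54% to 82% in secondary hypertension. That range is illustrative and assumes a constant hazard.

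Fairness between regimens is conditional. It needs similar causality attribution and a similar mix of 52-week and 104-week patients, and the plan secures neither. The ratios of 1.10 to 1.60 show what assumed differences would do; they do not estimate a bias in this trial.

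**What to change.** In SAP 1.2.7, replace the single SAE summary with two outputs.

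- **A.** All SAEs of any causality with onset after E1 completion, as protocol 9.5.3 defines it, and within the following 30 days, by regimen, organ class and preferred term. Name this table as the basis of the safety assessment. The explicit start keeps SAEs from E1 itself out of the table.
- **B.** SAEs with onset after day 30, in a separate table or listing labelled *investigator-suspected SAEs only*, with the narratives that protocol 9.5.3 provides for. State that all-cause SAE frequency after day 30 is not estimated.

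As a minor separate correction, remove from SAP 1.2.3 the assumption that worsening of ongoing E1 adverse events will be reported as new events, and say that non-serious worsening is not captured in E2.

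The cost is SAP wording and one extra shell, with no new data. Protocol 7.2 already requires the causality assessment, and its 30-day rule already depends on when the event occurred. The downside is fewer events in the main table.

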#### **Clinical chemistry**

Laboratory data will be summarized in SI units at baseline, visit LT 18 (week 104), and visit LT 19 (week 156) for absolute values and changes from baseline by treatment regimen. Serum creatinine, blood urea (BUN), sodium, potassium, chloride and calcium will be measured at LT Visits 18 (week 104) and 19 (week 156) (patients with secondary hypertension only). As the evaluations are only specified for patients with secondary

hypertension as per protocol, only patients with secondary hypertension will be included in the summary tables.

The incidence of patients with notable BUN, creatinine, sodium, potassium, chloride, and calcium values based on pre-specified percent change from baseline (defined in [Table 1-1](#) below) will be summarized. In addition, shift tables, based on normal ranges, from baseline to post-baseline assessments will be provided by treatment regimen. Listings of patients with notable laboratory values based on pre-specified percent change from baseline will be provided by laboratory parameter, treatment regimen, and patient number.

**Table 1-1 Notable Laboratory Abnormalities**

Parameter	Conventional Alert Value	Conventional Units	SI Alert Value	SI Units
Chemistry				
BUN	>50% increase	mg/dL	>50% increase	mmol/L
Creatinine	>50% increase	mg/dL	>50% increase	umol/L
Sodium	>5% increase	mEq/L	>5% increase	mmol/L
Potassium	>20% increase, >20% decrease, or any value >5.3	mEq/L	>20% increase, >20% decrease, or any value >5.3	mmol/L
Chloride	>10% increase, >10% decrease	mEq/L	>10% increase, >10% decrease	mmol/L
Calcium	>10% increase, >10% decrease	mg/dL	>10% increase, >10% decrease	mmol/L

In addition, the number and percentage of patients with clinically significant values (BUN: >14.28 mmol/L; creatinine > 176.8 µmol/L; potassium <3.5 mmol/L, > 5.5 mmol/L, or ≥ 6 mmol/L) at any post-baseline laboratory evaluation will also be presented.

In addition, clinical chemistry data will be listed by patient and treatment regimen.

### 1.3 Determination of sample size

All patients who successfully complete CSPP100A2365 and 2365E1 studies were offered enrolment into the study CSPP100A2365E2 for 52 or 104 weeks follow-up.

#### Appendix 1: SAS code for ANCOVA model

```

ods graphics on;
proc mixed data=one;
  class treatment region age etiology;
  model change = treatment region age etiology baseline_covariate /
solution residual;
  estimate 'Aliskiren vs Enalapril' treatment 1 -1/CL;
run;
ods graphics off;

```
